## Study information

Title	The real world evidence on treatment patterns, effectiveness, and safety of drugs for stroke prevention in nonvalvular atrial fibrillation patients in Korea
Protocol number	X9001134
Protocol version identifier	V.3.0
Date of last version of protocol	03 May 2018
Active substance	Apixaban ((PF-04652577/BMS-562247) (617001ATB, 617002ATB)
Medicinal product	ELIQUIS®
Research question and objectives	
This study seeks to address the following objectives:
 

● To explore baseline characteristics and drug utilization patterns in patients with nonvalvular atrial fibrillation (NVAF) newly prescribed with anti-thrombotic therapies.

● To compare the effectiveness of anti-thrombotic therapies in patients with NVAF

● To compare the safety of anti-thrombotic therapies in patients with NVAF

Country(-ies) of study	South Korea
Author	PPD [REDACTED] PharmD PPD [REDACTED] PPD [REDACTED], Pfizer Korea

	PPD
	PPD
	PPD , MPharm, MA, PhD
	PPD
	PPD
	PPD
	PPD

## 1. LIST OF ABBREVIATIONS

Abbreviation	Definition
AIDS	Acquired immune deficiency syndrome
CABG	Coronary Artery Bypass Graft surgery
CHA 2 DS 2 -VASc	Clinical stroke risk prediction tool based on comorbidities of congestive heart failure, hypertension, elderly age, diabetes mellitus, prior stroke or thromboembolism, vascular disease, and gender.
HAS-BLED	Clinical major bleeding risk score based on comorbidities of hypertension, abnormal renal and liver function, prior stroke, bleeding history, labile international normalized ratio values of anticoagulation level, elderly age, and concomitant drug or alcohol use.
HIRA	Health Insurance Review & Assessment Service
HIV	Human immunodeficiency virus
ICD-10	International Classification of Diseases 10 th revision
ICJME	International Committee of Medical Journal Editors
KCD-6	Korean Standard Classification of Diseases 6 th revision
KCD-7	Korean Standard Classification of Diseases 7 th revision
MI	Myocardial infarction
MPR	Medication possession ratio
NOAC	Non vitamin K antagonist oral anticoagulants
NSAIDs	Nonsteroidal anti-inflammatory drugs
NVAF	Nonvalvular atrial fibrillation
OAC	Oral anticoagulants
PCI	Percutaneous coronary intervention

Abbreviation	Definition
PPI	Proton pump inhibitor
TE	Thromboembolism
TIA	Transient ischemic attack

### 3. ABSTRACT

**Study title:** Real world evidence on treatment patterns, effectiveness, and safety of drugs for stroke prevention in nonvalvular atrial fibrillation patients in Korea (Version 2.0, 10 Oct 2017)

PPD

#### ***Rationale and Background:***

There have been far fewer real world studies on effectiveness and safety outcomes of antiplatelet therapy, warfarin and Non vitamin K antagonist oral anticoagulants (NOACs) in Asian populations. The nationwide claims database in Korea can provide an opportunity to study comparative effectiveness and safety outcomes of therapies to prevent thromboembolic events in patients with nonvalvular atrial fibrillation.

#### ***Research question and objectives:***

***Research question:*** What is the real world data on antiplatelet therapy, warfarin and NOACs that can be found in the nationwide claims database in Korea?

#### ***Primary objectives***

1. To explore baseline characteristics and drug utilization patterns in patients with nonvalvular atrial fibrillation (NVAF) who newly initiated NOACs, warfarin, or used aspirin
2. To compare effectiveness including hemorrhagic stroke, ischemic stroke and systemic embolism of antithrombotic therapies in patients with NVAF with the following antithrombotic therapies: NOACs, warfarin, and aspirin
3. To compare safety including major bleeding of antithrombotic therapies in patients with NVAF with the following antithrombotic therapies: NOACs, warfarin, and aspirin

*[NOTE] Comparative analyses will be performed contingent on a feasibility assessment based on the descriptive analyses*

#### ***Secondary objectives***

1. To explore and understand more detailed drug utilization patterns
  - o Standard doses versus reduced doses of NOACs

- Patterns of usage (i.e., switching, discontinuation) and clinical events preceding the pattern
- Compliance (i.e., medication possession ratio)

2. To compare effectiveness and safety of antithrombotic therapies versus not using therapies among low risk patients (low score of CHA2DS2-VASc)

**Study design:** Retrospective cohort study

**Population:** Subjects with atrial fibrillation diagnosed (from January 1, 2007 up to and including the index date\*) who newly initiated antithrombotic therapies (NOACs (not including edoxaban), warfarin, or used aspirin) between July 1, 2015 and November 30, 2016 in the Korean Health Insurance Review & Assessment Service (HIRA) database

*\*Index date is the first prescription date of study drugs, including NOACs, warfarin, and aspirin during the intake period (from July 1, 2015 to November 30, 2016).*

**Variables:**

Exposure: The exposure to the following will be considered:

1. Aspirin
2. Aspirin-clopidogrel combination\*
3. Clopidogrel\*
4. Warfarin
5. NOACs
  - Apixaban, Rivaroxaban, Dabigtran

\*[Note] Clopidogrel, Aspirin-clopidogrel will be included in descriptive analysis.

Outcome variables: The following outcomes will be assessed:

1. Effectiveness outcomes
  - Primary outcome: Composite of hemorrhagic stroke, ischemic stroke, and systemic embolism
  - Secondary outcomes: Individual outcome of hemorrhagic stroke, ischemic stroke, and systemic embolism
2. Safety outcomes

- Primary safety outcome: Major bleeding including gastrointestinal bleeding or intracranial bleeding and other bleeding
- Secondary safety outcomes: Individual outcome of major bleeding

**Key-Covariates:** Variables, including, but not limited to, will be age, sex, types of health insurance, CHA2DS2-VASc score, HAS-BLED score, Charlson Comorbidity Index score, etc.

**Data sources:** The Korean Health Insurance Review & Assessment Service (HIRA) database from January 1, 2007 to November 30, 2016 will be used for the analysis. The HIRA database contains the data of universal health insurance system in Korea. The database contains patients' demographic information, their use of inpatient and outpatient services, and pharmacy dispensing claims.

**Study size:** Based on HIRA disease statistics, the number of patients with atrial fibrillation (KCD code: I48) were 148,130 and 169,259 in 2015 and 2016, respectively. Thus, the anticipated number of patients will be approximately 150,000 since we plan to include patients who already had atrial fibrillation and were prescribed with aspirin, warfarin, or NOACs from July 1, 2015 to November 30, 2016. However, the study size might change after applying inclusion and exclusion criteria.

**Data analysis:** Patients will be matched on demographic and clinical characteristics. All outcome variables will be summarized descriptively through the tabular and graphical display of mean values, medians, ranges, and standard deviations of continuous variables of interest and frequency distributions for categorical variables. Effectiveness and safety outcomes of treatments will be estimated from time-to-event models. The 95% confidence intervals for the estimates will be calculated and  $p < 0.05$  will be considered significant. All analyses will be carried out using SAS version 9.4. Analysis and reporting will be compliant with Strengthening the Reporting of Observational Studies in Epidemiology (STROBE) recommendations.

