Individual outcome of primary outcome	Secondary effectiveness outcome	HIRA database	
Claims with the following KCD codes in all diagnosis codes (main and sub-diagnosis codes) whichever came first (i.e., the first occurred event will be used):
 
 
1. Ischemic stroke: G459, I63, I693
 
2. Systemic embolism: I74
 
3. Hemorrhagic stroke: I60, I61, I62, I690, I691, I692
 
 
[NOTE] Hospitalization and CT or MRI codes (brain CT or MRI for ischemic stroke and hemorrhagic stroke; any CT or MRI for systemic embolism) were also required for identification. For CT or MRI codes, please see above.

Major bleeding	Primary safety outcome	HIRA database	
Bleeding requiring hospitalization will be identified using hospital claims which had a bleeding diagnosis code as the first occurred KCD code and it will be consisted of intracranial hemorrhage (ICH) and gastrointestinal (GI) bleeding, and other bleeding. All KCD diagnosis codes (main and sub-diagnosis codes) will be used. Especially, hospitalization and brain CT or MRI codes will be needed to identify ICH.
 
 
- Intracranial (I60, I61, I62, I690, I691, I692, S064, S065, S066, S068)
 
- Gastrointestinal bleeding (I850, I983, K2211, K226, K228, K250, K252, K254, K256, K260, K262, K264, K266, K270, K272, K274, K276, K280, K282, K284, K286, K290, K3181, K5521, K625, K920, K921, K922)
 
- Other bleeding (D62, H448, H3572, H356, H313, H210, H113, H052, H470, H431, I312, N020-N029, N421, N831, N857, N920, N923, N930, N938, N939, M250, R233, R040, R041, R042, R048, R049, T792, T810, N950, R310, R311, R318, R58, T455, Y442, D683)
 

Individual outcome of major bleeding	Secondary safety outcome	HIRA database	
Individual outcome of ICH (diagnosis codes in all main and sub-diagnosis codes + hospitalization + brain CT or MRI), gastrointestinal bleeding (diagnosis codes in all main and sub-diagnosis codes + hospitalization), and other bleeding (diagnosis codes in all main and sub-diagnosis codes + hospitalization).
 
For codes, please see above.

Variable	Role	Data source(s)	Operational definition
Types of health insurance	Covariates	HIRA database	Types of health insurance divided as the following: 1. National Health Insurance 2. Medical aid

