CHA 2 DS 2 -VASC	Covariates	HIRA database	CHA 2 DS 2 -VASC as continuous data or dichotomous data. The score will be calculated using the following KCD codes (refer to SAP-Appendix 2, Table 9): 1. Congestive heart failure 2. Hypertension 3. Diabetes mellitus 4. Stroke/TIA/TE 5. Vascular disease 6. Age $\geq$ 75 7. Age 65-74 8. Sex (female)
HAS-BLED	Covariates	HIRA database	HAS-BLED as continuous data or dichotomous data. The score will be calculated using the following KCD codes (refer to SAP-Appendix 2, Table 10): 1. Hypertension 2. Abnormal renal function 3. Abnormal liver function 4. Stroke 5. Bleeding history or predisposition 6. Age $>$ 65 7. Antiplatelet or NSAID use 8. Alcoholism
Charlson Comorbidity Index	Covariates	HIRA database	Charlson Comorbidity Index as continuous data or dichotomous data. The index will be calculated using the following KCD codes (Refer to SAP-Appendix 2, Table 11): 1. Myocardial infarction 2. Congestive heart failure 3. Peripheral vascular disease 4. Cerebrovascular disease 5. Dementia 6. Chronic pulmonary disease 7. Rheumatic disease 8. Peptic ulcer disease 9. Mild liver disease 10. Diabetes without chronic complication 11. Diabetes with chronic complication 12. Hemiplegia or paraplegia 13. Renal disease 14. Any malignancy, including lymphoma and leukemia, except malignant neoplasm of skin 15. Moderate or severe liver disease 16. Metastatic solid tumor 17. AIDS/HIV

Variable	Role	Data source(s)	Operational definition
Medication use	Covariates	HIRA database	
It will be consisted of the following:
 
 
1. History of NSAIDs
 
2. History of antiplatelet
 
3. History of PPI
 
4. History of H2-receptor antagonists
 
5. History of antiarrhythmics
 
6. History of digoxin
 
7. History of statins
 

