## 8.4 Data sources

South Korea has a universal health coverage system that the National Health Insurance covers approximately 97% of the overall South Korean population. The claims data of Health Insurance Review & Assessment Service (HIRA) contains 46 million patients per year that account for 90% of the total population in Korea and include claims from almost 80,000 healthcare service providers across South Korea as of 2011.

The claims data of HIRA includes patients' diagnosis, treatment, procedures, surgical history, and prescription drugs which provide a valuable resource for healthcare service research. Data elements captured in the HIRA database include patient-level demographic and plan enrollment information (e.g., start and stop dates of health plan enrollment), date-stamped (month and year) inpatient and outpatient medical claims (e.g., diagnosis codes, procedure codes, provider specialty), and pharmacy claims (e.g., prescription fill/refill dates, drug name/code, dosage). While procedure codes that identify patient receipt of laboratory tests are available, actual laboratory values and test results are not available.

The HIRA database has unique attributes that make it a useful data source for this study. The key advantage of the HIRA database relative to other potential data sources (e.g., medical chart review) is that it is a population level data including most of Korean population and it will provide a large analytic sample and provide accurate claim-level treatments pattern and health care utilization across all provider settings (e.g., inpatient, outpatient, pharmacy) in patients' spectrum of care.

One key limitation of the HIRA database is that it does not include clinical variables such as laboratory values and clinical markers. To overcome this limitation, the Charlson comorbidity index and overall healthcare utilization observed during the pre-index period will be used as proxy measures to incorporate the overall health status of the individual patients.

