## 8.7 Data analysis

- All outcome variables will be summarized descriptively through the tabular and graphical display of mean values, medians, ranges, and standard deviations of continuous variables of interest and frequency distributions for categorical variables.
- Patients with aspirin, warfarin, and NOACs will be matched via propensity-score method. Patients will be matched on patient demographics (i.e., age, sex) and clinical (i.e., CHA2DS2-VAsC score, Charlson Comorbidity Index score, etc) variables. Other propensity score method (i.e., covariate adjustment, inverse probability of treatment weighting (IPTW)) will also be used. A Cox proportional hazards model, to account for differences in follow-up time and right data censoring, will be used to compare effectiveness and safety outcomes between treatment groups.
- Comparative analyses will be performed contingent on a feasibility assessment based on the descriptive analyses
- All analyses will be carried out using SAS version 9.4. The 95% confidence intervals for the estimates will be calculated and p < 0.05 considered significant.
- Sensitivity analysis of performing IPTW using the propensity score derived from multinomial model will be conducted.

Detailed methodology for summary and statistical analyses of data collected in this study will be documented in a Statistical Analysis Plan (SAP), which will be dated, filed and maintained by the sponsor. The SAP may modify the plans outlined in the protocol; any major modifications of primary endpoint definitions or their analyses would be reflected in a protocol amendment.

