4.4 COVARIATES

Table 4. Baseline Variables

Variable	Role	Operational definition
Age	Baseline characteristic and potential confounder	Age at index date
Sex	Baseline characteristic and potential confounder	
 1. Male 2. Female
Types of health insurance	Baseline characteristic and potential confounder	
Types of health insurance divided as the following:
 
 1. National Health Insurance 2. Medical aid

NIS Protocol <X9001134>
 Statistical Analysis Plan
 <Version 3.0> <03 May 2018>

Variable	Role	Operational definition
CHA ₂ DS ₂ -VASC	Baseline characteristic and potential confounder	
CHA₂DS₂-VASC as continuous data or dichotomous data. The score will be calculated using the following KCD codes (Appendix 2, Table 9):
 
 1. Congestive heart failure 2. Hypertension 3. Diabetes mellitus 4. Stroke/TIA/TE 5. Vascular disease 6. Age ≥ 75 7. Age 65-74 8. Female
HAS-BLED	Baseline characteristic and potential confounder	
HAS-BLED as continuous data or dichotomous data. The score will be calculated using the following KCD codes (Appendix 2, Table 10):
 
 1. Hypertension 2. Abnormal renal function 3. Abnormal liver function 4. Stroke 5. Bleeding history or predisposition: refers to any bleeding codes 6. Age > 65 7. Antiplatelet or NSAID use 8. Alcoholism 
[Note] Labile international normalized ratio is not available in HIRA data and does not apply to patients on aspirin, or NOACs, so the modified HAS-BLED score has a maximum value of 8 instead of 9.

Charlson Comorbidity Index	Baseline characteristic and potential confounder	Charlson Comorbidity Index as continuous data or dichotomous data. The index will be calculated using the following KCD codes (Appendix 2, Table 11):

NIS Protocol <X9001134>
Statistical Analysis Plan
<Version 3.0> <03 May 2018>

Variable	Role	Operational definition
		
1. Myocardial infarction2. Congestive heart failure3. Peripheral vascular disease4. Cerebrovascular disease5. Dementia6. Chronic pulmonary disease7. Rheumatic disease8. Peptic ulcer disease9. Mild liver disease10. Diabetes without chronic complication11. Diabetes with chronic complication12. Hemiplegia or paraplegia13. Renal disease14. Any malignancy, including lymphoma and leukemia, except malignant neoplasm of skin15. Moderate or severe liver disease16. Metastatic solid tumor17. AIDS/HIV

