5 STATISTICAL METHODOLOGY AND STATISTICAL ANALYSES

5.1 STATISTICAL METHODS

Descriptive Analysis:

- All outcome variables will be summarized descriptively through the tabular and graphical display of mean values, medians, ranges, and standard deviations for continuous variables of interest and frequency distributions for categorical variables.
- The proportion of antithrombotics (aspirin, clopidogrel, aspirin and clopidogrel combination, warfarin, NOACs) at index date will be examined.
- Appropriate tests (e.g., t-test, chi-square test) will be used based on the distribution of the measure. The $p < 0.05$ considered significant.

Multivariate Analysis:

Propensity score method

The estimation of propensity score will be performed to control for confounders in each sub-dataset: (1) each NOAC versus NOAC; (2) each NOAC versus warfarin; (3) each NOAC versus aspirin.

Propensity scores are estimated by logistic regression analyses that incorporate potential treatment predictors as independent variables and types of index treatment as dependent variable (e.g., apixaban=1, warfarin=0). Covariates in the logistic regression model will

include variables such as age, sex, CCI score, CHA₂DS₂-VASc score, HAS-BLED score, and comorbidities, but the final list of these covariates will be discussed and determined after reviewing the results of descriptive analysis of the pre-matched datasets. Further, we will report the *c*-statistic of the propensity score that indicates the degree to which the propensity score model discriminates between treated patients and untreated patients.

After estimation of propensity score, we will perform propensity score matching (PSM). 1:1 matching without replacement will be performed.

The populations would be first matched using PSM according to their index treatment. For these matched populations we should then explore the proposed subgroups by: making an assessment of patient numbers in the subgroups and checking that patient characteristics are still similar between the index treatments in the subgroups. If they are similar, then conduct interaction term analysis is being conducted to determine whether the treatment effect varies between the subgroups. If the populations are no longer similar in characteristics, then re-matching via PSM will be performed for the subgroups.

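### Whether the index drug was started in hospital or as an outpatient is in no covariate list, and neither is the promised pre-index healthcare utilization, so an imbalance in either could go unseen

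*Protocol*

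**What the plan says.** The protocol abstract (Key-Covariates) begins "Variables, including, but not limited to, will be age, sex, types of health insurance" and goes on to CHA2DS2-VASc, HAS-BLED and Charlson scores, ending with an open 'etc.'. Protocol 8.3 lists insurance type, the three scores and seven drug histories, starting with "History of NSAIDs". Protocol 8.7 states "Patients will be matched on patient demographics (i.e., age, sex) and clinical" variables. SAP Table 4 (section 4.4) repeats the abstract's variables and adds baseline medication. SAP 5.1 says the propensity model will "include variables such as age, sex, CCI score", the other two scores and comorbidities, and that the final list will be settled after the descriptive results of the unmatched datasets have been reviewed. Table 5, the baseline shell, is marked as an example.

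On the data, Protocol 8.4 lists "inpatient and outpatient medical claims (e.g., diagnosis codes, procedure codes, provider specialty" among the HIRA elements. Because laboratory values are missing, the same section says the Charlson index and "overall healthcare utilization observed during the pre-index period will be used as proxy measures" of health status. SAP 2.1 repeats both statements.

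On balance, SAP 5.1 applies a standardized-difference limit of 0.1 to all covariates, and SAP 5.2 uses 10% after matching.

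**The concern.** A drug started during an admission often follows an acute event. Such a start can mark a higher short-term risk of stroke or bleeding, and it may also bear on which drug is chosen. A variable related to both is a confounder, and this one is in the data. The limitation on unobserved confounders in Protocol 8.9.5 therefore does not cover it.

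The comparisons with aspirin (sub-datasets 7 to 9) give a particular reason to look. NOAC users must be free of oral anticoagulants in the preceding year, while aspirin users may have had anticoagulants or antiplatelets. An aspirin index date can therefore be a routine repeat prescription, while a NOAC index date is a new start after at least a year without anticoagulants. The mix of inpatient and outpatient index prescriptions could differ for that reason alone.

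At stake is residual confounding in the hazard ratios for stroke/systemic embolism and major bleeding, with a balance table that looks clean because it has no row that would reveal the problem.

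**Working it through.** **Step 1: look for the variables in every list.**

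| Place | Index setting named? | Pre-index utilization named? |
|---|---|---|
| Protocol abstract, Key-Covariates | No | No |
| Protocol 8.3 | No | No |
| Protocol 8.7 | No | No |
| SAP Table 4 | No | No |
| SAP 5.1, propensity covariates | No | No |
| SAP 5.2 | No | No |
| SAP 6, summary of analyses | No | No |
| SAP Table 5 (example shell) | No | No |

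Utilization appears only in the data-source text (Protocol 8.4, SAP 2.1), where its use is promised.

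**Step 2: ask whether the listed variables already carry the information.** SAP Table 9 gives 2 points for stroke. SAP Table 10 gives 1 point for stroke and 1 for bleeding history. Each is present or absent. The documents state no look-back window for these scores; the baseline and pre-index windows they define elsewhere are 12 months or 1 year. Even with a 12-month window, a stroke eleven months before an outpatient start and a stroke shortly before an inpatient start score the same.

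**Step 3: illustrate the size.** The plan has no figure of its own on this point to reproduce. For a binary covariate left unbalanced, with true HR = 1.00:

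apparent HR = [1 + p1(R − 1)] / [1 + p0(R − 1)]

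Here p1 and p0 are the shares of inpatient starts in the two arms, and R is the event-rate ratio of inpatient to outpatient starters given the listed covariates. All three are assumptions.

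| p1 vs p0 | R = 1.5 | R = 2 | R = 3 |
|---|---|---|---|
| 20% vs 15% | 1.100/1.075 = 1.02 | 1.20/1.15 = 1.04 | 1.40/1.30 = 1.08 |
| 30% vs 15% | 1.150/1.075 = 1.07 | 1.30/1.15 = 1.13 | 1.60/1.30 = 1.23 |

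If the other arm has more inpatient starts, the factors invert: 1/1.02 = 0.98 to 1/1.23 = 0.81. If p1 = p0, the factor is 1.00.

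**Step 4: would the SAP's limit catch this if setting were a covariate?** The standardized difference is (p1 − p0) / √{[p1(1 − p1) + p0(1 − p0)]/2}.

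- 20% vs 15%: 0.05 / √[(0.1600 + 0.1275)/2] = 0.05/0.379 = 0.13
- 30% vs 15%: 0.15 / √[(0.2100 + 0.1275)/2] = 0.15/0.411 = 0.37

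Both exceed 0.1, so the existing rule would flag even the smaller imbalance, but only if the variable is measured.

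**The case against.** The lists are open by their own wording, the final propensity list is deferred, and Table 5 is only an example. The team could add setting without departing from the plan. This stands: the supportable statement is that these variables are not named, not that they will go unbalanced. But permission is not a plan, and nothing written would prompt anyone to look.

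The utilization proxy, if used, would capture some recent acute illness, and comorbidities such as stroke/TIA and bleeding may balance part of the rest. This also stands in part. Utilization would help only if it reached the model, and it does not describe the index prescription itself.

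A reader might infer that prescriber specialty belongs in every model too. The documents do not support that. Protocol 8.4 attaches specialty to medical claims, and its examples of pharmacy-claim elements do not include it, so a link to the index prescription is not shown. If specialty predicts the drug but has little effect of its own on outcome, adding it costs precision and can amplify residual confounding.

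A reader might also infer biased detection, because Protocol 8.3 requires "Hospitalization and CT or MRI codes" for stroke and systemic embolism. That rule applies alike to all arms, so by itself it shows no difference between them.

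**Conclusion.** The omission is confirmed in every list, for both index setting and the promised utilization measure. It is a worthwhile, inexpensive improvement and not a demonstrated bias. Under the stated assumptions (20% to 30% against 15% inpatient starts, rate ratio 1.5 to 3 given the listed covariates), a true HR of 1.00 would appear as about 1.02 to 1.23, or 0.98 to 0.81 if the imbalance runs the other way. The documents give neither the actual imbalance nor its direction.

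It would go too far to call setting a strong marker of drug choice, or to say that confounding remains in all nine comparisons. No section relates setting to drug choice or outcome. The design gives a specific reason for concern in the aspirin comparisons but none for NOAC against NOAC.

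**What to change.** 1. Add two variables to SAP Table 4 and Table 5: setting of the index prescription (inpatient or outpatient), and pre-index healthcare utilization, for example any admission in the 12-month baseline. State how the index prescription is assigned to a setting, since Protocol 8.4 describes medical claims as dated by month and year.
2. Include both in the pairwise propensity models and in the multinomial sensitivity model, and hold both to the existing 0.1 standardized-difference limit.
3. Show prescriber specialty as a descriptive row, with an optional sensitivity analysis, only if it can be linked to the index prescription.

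The cost is SAP wording, one or two derived variables from claims already requested, and possibly slightly fewer matched patients. This does not replace a rule for outcome codes recorded during the index admission; that is a separate matter, which a covariate cannot settle.
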